3.5. VULNERABLE SUBJECTS

Vulnerable subjects will not be included in the study. Children, pregnant women, nursing home residents, and persons with limited autonomy or decisional incapacity are examples of vulnerable subjects that will not be included in the study.

**THE SAFETY AND EFFICACY OF BROADBAND LIGHT (BBL) TREATMENT
FOR REFRACTORY DRY EYE DISEASE (DED)**

4. STUDY DESIGN

This is a prospective, open-label trial to evaluate the safety and efficacy of BBL treatment for DED. A minimum of twenty subjects with DED and meibomian gland dysfunction (MGD) will be enrolled at one clinical site. The enrolled subjects will already be in need of medical treatment for refractory DED, where refractory is defined as having failed (persistent dry eye signs and or symptoms) after at least one prior DED treatment modality. All subjects will undergo a full ophthalmic exam, DED diagnostic testing, and BBL treatment procedure.

The Clinical Investigator and study staff will recruit subjects for study participation. The Clinical Investigator will screen subjects to determine enrollment eligibility. If the subject selection criteria are met, informed consent will be obtained, and each subject will be assigned a unique enrollment identification number and will be randomized by coin flip into protocol 1 or 2. They will immediately proceed to the run-in phase, where the subjects will undergo a full ophthalmic exam and DED diagnostic testing. Additionally, clinical photographs of the face, eyes, and meibomian glands will also be collected, and subjects will complete DED questionnaires (the Standardized Patient Evaluation of Eye Dryness (SPEED) questionnaire and Visual Analogue Scale (VAS)).

Two weeks following the screening visit, subjects will visit the clinical site on a once per month basis (or within a four day visit window) to initiate the treatment phase of the study. Subjects will undergo a full ophthalmic exam, DED diagnostic testing, collection of photographs, and complete self-reported questionnaires. Subjects will undergo the BBL treatment, which consists of topical anesthetic application, and subsequent BBL administration to the malar and periorbital region (Figure 1). The completion of three treatment passes defines the clinical endpoint of BBL treatment. The subjects will complete a series of three treatments at monthly intervals (with a 1 week visit window).

One month following the completion of the series of three BBL DED treatments, the subjects will return to the clinical site for the follow-up visit. All subjects will undergo a full ophthalmic exam, DED diagnostic testing, collection of photographs, and completion of self-reported questionnaires.

5. STUDY METHODS AND PROCEDURES

For all enrolled subjects, the study will be divided into three sections – (1) study screening, (2) treatment, and (3) follow-up periods:

5.1. SCREENING (TWO WEEKS)

Subject screening (study week minus two weeks) is designed to determine whether the subjects are eligible for study enrollment and to facilitate completion of the run-in period. The Clinical Investigator and study staff will recruit subjects by offering participation to existing patients at the evaluation site and by referrals. Eligible subjects are defined as those that meet all the Inclusion Criteria and meet none of the Exclusion Criteria. During subject screening and enrollment the following information will be collected:

- Evaluation of subject eligibility
- Fitzpatrick skin type
- A complete medical history
- A complete ophthalmic history
- Information on all concomitant medications

THE SAFETY AND EFFICACY OF BROADBAND LIGHT (BBL) TREATMENT FOR REFRACTORY DRY EYE DISEASE (DED)

- Clinical photographs of face, eyes, and meibomian glands before treatment
- Persistent dry eye signs and or symptoms after at least one prior DED treatment modality
- Signed Informed Consent Form

At the discretion of the Clinical Investigator, subjects who fail screening may be re-screened once, at a later date once the subject has met the criteria. The Clinical Investigator or study staff will obtain the signed informed consent form before any study specific procedures are performed. Each subject will be assigned a unique screening number, which will correspond to his/her unique enrollment identification number.

Potential subjects will be given ample time to ask questions and get their questions answered in regards to their participation in the study. The questions will be answered in a manner that is understandable to the subject. Subjects will be told that whether or not they choose to participate in the study, it will not affect their relationship with their physician.

After eligibility is confirmed the subject will immediately proceed to the run-in phase. This phase will be completed to ensure complete collection of subject baseline values. Subjects will be instructed not to use any artificial tears for at least 2 hours before testing. They will also be instructed to continue any over-the-counter habitual artificial tears at the same frequency and will be instructed not to change any of their current therapy for their DED. All subjects will undergo a full ophthalmic exam and DED diagnostic testing, which will include clinical evaluations for Dry eye: All sites will perform osmolarity, and Inflammadry test strips for level of MMP-9, staining pattern on cornea (using oxford scale) with Fluorescein, Tear Break Up Time (TBUT), 5 minute Schirmer's testing with anesthesia. USC site will obtain swabs for evaluation of ocular surface microbiome, to be sent to a core facility.

Additionally, clinical photographs of the face, eyes, and meibomian glands will also be collected, and subjects will complete DED questionnaires (SPEED and VAS). All subjects will undergo BBL treatment for a series of 3 treatments after being randomized to treatment protocol 1 or 2 (protocol 1 includes 420nm and 560nm treatment settings, protocol 2 includes only 560nm treatment settings, see Table 2 below). To demonstrate effects of DED treatments, baseline values will later be compared to values following treatment.

5.2. BBL TREATMENT

The BBL system has FDA clearance for use in the treatment of benign pigmented lesions, cutaneous lesions, benign cutaneous vascular lesions, mild to moderate acne, and the temporary increase in local circulation. The treatments will consist of 3 such treatments, 3-5 weeks apart.

The BBL system is comprised of:

- Device console - The device console is connected to the footswitch, the cable arm for the treatment handpiece, and the user screen. The device console houses the light source and the power supply.
- Footswitch - The footswitch is connected to the device console. Footswitch depression by the clinician enables energy delivery.

THE SAFETY AND EFFICACY OF BROADBAND LIGHT (BBL) TREATMENT FOR REFRACTORY DRY EYE DISEASE (DED)

- Cable arm - The cable connects the device console and the treatment handpiece. The cable provides free range of motion for the treatment handpiece.
- Handpiece - The handpiece is connected to the cable arm, and steers the pattern of energy onto the patient.
- User Screen - The user screen is connected to the console, and serves as an interface to allow the clinician to select different treatment parameters.

5.2.1. ANESTHETIC APPLICATION

For the skin of the malar region, topical anesthetic consisting of lidocaine cream is applied for 30 minutes prior to treatment.

The subject's head will be tilted back and the eyelid pulled away from the eye. A single drop of an ophthalmic solution USP, of 1% proparacaine hydrochloride will be administered into the eye as a local anesthetic. With a single drop, the onset of anesthesia begins within thirty seconds and persists for fifteen minutes or longer.

5.2.2. PREPARING THE SUBJECT FOR TREATMENT

Protective eye shields to safeguard against light exposures will be provided to the subjects and personnel in the treatment room will wear protective goggles. The patient eye shields will remain in place until after the completion of the treatment. For the subject, protective opaque metal eye shields will be placed on the surface of the eye, covering the entire cornea and fitting inside the palpebral fissure (eyelids) to protect from exposure to the BBL light.

To prepare the subject and the BBL device for treatment:

- Disinfect the treatment handpiece
- Cleanse treatment area skin with alcohol
- Confirm absence of recent sun exposure on the subject's skin
- Apply topical lidocaine cream to malar skin and eyelids
- Instill 1% Proparacaine into each eye
- Place protective metal eye shields onto ocular surface
- Apply a thin layer of ultrasound gel over the entire treatment area (malar skin)
- Select proper treatment settings. The settings will vary by subject's Fitzpatrick Skin Type and randomization (refer to BBL safe start settings Table 1).
- Select the appropriate filter and insert into treatment handpiece
- Place the appropriate adapter over the sapphire crystal on the treatment handpiece

5.2.3. TEST SPOT

On a site located below the hairline near the tragus, a test spot will be performed to assess the clinical response of the epidermis. After delivery of one pulse, the ultrasound gel is removed and the test spot is assessed. Treatment settings (Table 1) are then adjusted as indicated by the epidermal response. If the reaction is too severe (intense erythema, purpura, immediate white skin), settings should be decreased in intensity by the following actions in the following order:

1. Decrease fluence by 1-5 J/cm²
2. Increase pulse width by 5-10 msec
3. Decrease cooling temperature 5-10°C

**THE SAFETY AND EFFICACY OF BROADBAND LIGHT (BBL) TREATMENT
FOR REFRACTORY DRY EYE DISEASE (DED)**

5.2.4. TREATMENT AREA

The BBL treatment will be delivered on the malar and periorbital region of the face (see Table 2 and Figure 1 below).

The BBL treatment will be delivered following treatment parameters described in Table 2:

1. Using the 15 x 15 mm adapter, fire pulses across the malar treatment area (Figure 1).
2. Using the 3 or 7mm round adapter, fire pulses across both lower eyelids and upper eyelids, while shielding the eyelashes.
3. Protocol 1 includes two malar treatment passes at 420 and one lower eyelid pass at 420nm, followed by one malar treatment pass at 560nm and one upper and lower eyelid treatment pass at 560nm.
4. Protocol 2 includes two treatment passes at 560nm and one upper and two lower eyelid treatment passes at 560nm.

5.2.5. POST BBL TREATMENT OBSERVATIONS AND INSTRUCTIONS

- Erythema – Erythema may be apparent for several hours after treatment.
- Sunscreen – Sunscreen with at least SPF 30 is recommended on the facial treatment locations for at least two weeks following each BBL treatment.

5.3. FOLLOW UP VISIT AFTER COMPLETION OF TREATMENT SERIES (FOUR WEEKS POST TREATMENT)

Four weeks following the final BBL treatment, the subjects will return to the clinical site for the follow up visit. The subject will undergo a full ophthalmic exam and the same DED diagnostic measurements and tests that were done at baseline. Photographs of the subject's face, eyes, and meibomian glands will also be collected. Subject questionnaires will be completed.

6. RISK AND BENEFIT ASSESSMENT

There are both risks and benefits associated with enrollment and treatment in the clinical study.

6.1. POTENTIAL RISKS OF TOPICAL ANESTHETIC USE ON EYE

There are both risks and complications associated with the application of anesthetics.

- Irritation – Temporary burning, stinging, or redness of the eye.
- Permanent corneal opacification and vision loss – under rare conditions of prolonged use.

6.2. POTENTIAL RISKS OF BROADBAND LIGHT TREATMENT

There are both risks and complications associated with the application of light treatments.

- Pain – This is a common adverse reaction and can be minimized by the use of anesthetic.
- Swelling – May occur around the eyes and bridge of the nose immediately after treatment.
- Purpura – May occur from having the pulse width too short and/or fluence too high during treatment, or from the concomitant use of anticoagulant medications.
- Pigmentary changes – Hyperpigmentation or hypopigmentation may occur in the treatment area.
- Urticaria – In some subjects, a histamine or hive reaction may occur in the treatment area.
- Scarring – In rare occurrence following any intense pulsed light (IPL) treatment.

THE SAFETY AND EFFICACY OF BROADBAND LIGHT (BBL) TREATMENT FOR REFRACTORY DRY EYE DISEASE (DED)

[figure not shown]
- Lack of permanent results – Treatment may not completely improve or prevent future eye or skin symptoms. Additional medical procedures may still be necessary to further improve DED.
- Hair loss/eyelash thinning— Repeated treatment to hair follicles may result in reduction of hairs/eyelashes; care is taken during the procedure to block exposure to eyelash follicles.
- Intraocular damage and inflammation may occur if treating without proper eye shielding

6.3. POTENTIAL BENEFITS

The benefits of study enrollment and treatment are related to the objectives and endpoints of the study. The study aims to provide a safe and efficacious treatment to reduce or alleviate the signs and symptoms of DED.

7. TABLES AND FIGURES

7.1. FIGURE 1. SCHEMATIC OF BBL TREATMENT REGION

7.2. TABLE 1. BBL SAFE START TREATMENT SETTINGS

SKIN TYPE	BBL FILTER	FLUENCE (J/cm ²)	PULSE WIDTH (ms)	TEMPERATURE (°C)
I-II	420nm	7	200	20
III-IV	420nm	6	200	20
V	420nm	5	200	20
I-II	560nm	15	20	20
III-IV	560nm	13	20	20
V	560nm	11	20	20

1.1. TABLE 2. BBL TREATMENT PROTOCOL

THE SAFETY AND EFFICACY OF BROADBAND LIGHT (BBL) TREATMENT
FOR REFRACTORY DRY EYE DISEASE (DED)

Table 2a. Protocol 1: 420nm and 560nm filter

PASS	FILTER (nm)	FINESSE ADAPTER	ANATOMICAL REGION
1	420	15x15mm square	temple to temple
2	420	15x15mm square	temple to temple
3	420	3mm round	lower lid
4	560	15x15mm square	temple to temple
5	560	3mm round	Upper and lower lid

Table 2b. Protocol 2: 560nm filter only

PASS	FILTER (nm)	FINESSE ADAPTER	ANATOMICAL REGION
1	560	15x15mm square	temple to temple
2	560	15x15mm square	temple to temple
3	560	3mm round	lower lid
4	560	3mm round	Upper and lower lid

## Broadband Light for Refractory Dry Eye Disease Statistical Analysis Plan

The SPEED validated dry eye disease questionnaire and visual analog scale will be given to patients at time of enrollment and after three sessions, the mean score before and after treatment for all patients will be calculated along with standard deviation and a student's T test will be used to assess whether there is a significant difference ( $p<0.05$ ).

The same will be done for numbers such as tear osmolarity, basal tear production test times, tear break-up times. The proportion of patients in each category of the oxford scale for fluorescein grading (I-V) will also be compared at baseline and post-treatment and the change in grade of individual patients will be assessed descriptively.

For the microbiome portion of the study, swabs from the ocular surface and lid margin will be obtained, in addition to facial skin and environmental control, at baseline and after treatment. 16S ribosomal DNA sequencing will be performed to generate an amplicon sequence variant (ASV) table using DADA2. Briefly, DADA2 performs quality filtering, de-noising, sample inference, and chimera removal using an empiric error model to generate exact amplicon sequences. Next, taxonomies will be assigned to each sequence variant using the RDP naïve Bayes classifier. The 'decontam' R package

(<https://www.biorxiv.org/content/early/2017/11/17/221499>) will be used to remove contaminant sequences based on the composition of negative controls including both DNA extraction buffers and PCR negatives.

Principal coordinates analysis (PCoA) and permutational multivariate ANOVA will be used to assess for site-dependent effects of treatment on bacterial composition (eyelid margin vs. facial skin vs. environmental control). Alpha diversity will be measured using the Chao1 and Shannon indices, and beta diversity will be measured using Bray-Curtis, Jaccard, and Jenson-Shannon distances. Standard non-parametric methods (e.g. Wilcoxon rank-sum test, Kruskal-Wallis test) will be used to compare alpha and beta diversity metrics between various groups. Zero-inflated negative binomial (ZINB) regression will be used to identify specific bacterial taxa that are differentially abundant by site and treatment. We will also utilize random forest classification as an alternative approach to identify bacterial taxa that distinguish the groups. The Benjamini-Hochberg false discovery rate (FDR) method will be used to adjust all statistical comparisons for multiple hypotheses.

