3. CRITERIA FOR SUBJECT SELECTION

3.1. NUMBER OF SUBJECTS

In this prospective study to determine safety and efficacy, a minimum of twenty subjects will be treated to detect improvement after BBL treatment for DED.

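### The SAP compares before and after values in the same patients but names no paired or patient-blocked analysis, for the clinical outcomes or the swabs

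*SAP*

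**What the plan says.** **Clinical outcomes.** SPEED and VAS are given at enrolment and after the three sessions. The SAP's first paragraph then says that the "mean score before and after treatment for all patients will be calculated along with standard deviation and a student's T test" will be used, at p<0.05. Its second paragraph extends this: "The same will be done for numbers such as tear osmolarity, basal tear production test times, tear break-up times". Protocol 5.1 gives the purpose: "To demonstrate effects of DED treatments, baseline values will later be compared to values following treatment". Protocol 5.3 has each patient return four weeks after the last session for "the same DED diagnostic measurements and tests that were done at baseline". Protocol 3.1 says that "a minimum of twenty subjects will be treated to detect improvement after BBL treatment for DED".

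**Microbiome.** The SAP says that "swabs from the ocular surface and lid margin will be obtained, in addition to facial skin and environmental control, at baseline and after treatment". For the diversity measures, "Standard non-parametric methods (e.g. Wilcoxon rank-sum test, Kruskal-Wallis test) will be used to compare alpha and beta diversity metrics between various groups". Permutational multivariate ANOVA (PERMANOVA) is named for composition and zero-inflated negative binomial (ZINB) regression for taxa. Neither is given a patient block, stratum or random effect.

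No paired, signed-rank, repeated-measures or mixed-model method is named in either document. The only within-patient item is the change in each patient's Oxford grade, which is descriptive.

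**The concern.** Every before/after comparison has two values from one patient, and the swabs add several body sites from that patient. An analysis plan should make use of that structure. Here it is left open. Student's t test has a paired and a two-sample form, and two analysts could each follow the SAP faithfully and report different p-values from the same data. The requested summaries, a mean and SD at each time, do not give the SD of change, so a reader could not recover the paired result from them.

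For the swabs the wording leans further the wrong way. Rank-sum and Kruskal-Wallis treat all samples as independent, which is not so for before against after at one site, or for lid margin against facial skin in one patient.

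At stake is the precision of the before/after efficacy result in a study that may have only twenty patients.

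**Working it through.** **Nothing to reproduce.** The documents give a minimum of 20 patients and p<0.05. They give no effect size, SD, power or within-patient correlation, so what follows is an illustration.

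**Inputs**
- n = 20 patients with both values: the minimum in Protocol 3.1, assuming none is missing.
- Alpha 0.05 from the SAP; two-sided is assumed because the SAP does not say.
- Assumed: normal data, equal SD (set to 1) before and after, mean shift d = 0.6 SD, and correlation r between a patient's two values of 0, 0.3, 0.5 or 0.7.

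**Formulas**
- Variance of one patient's change: 2(1 − r).
- Paired t: noncentrality d√n / √(2(1 − r)), with n − 1 = 19 degrees of freedom. At r = 0.5 this is 0.6 × √20 / 1 = 2.68; against a critical value of 2.093 the noncentral t gives power of 72.1%.
- Two-sample t: takes the standard error as √(2/n) whatever r is, with 38 degrees of freedom. The true standard error is √(2(1 − r)/n), so the test overstates it by 1/√(1 − r): 1.20, 1.41 and 1.83 times at r = 0.3, 0.5 and 0.7. Its power and type I error were simulated (200,000 runs per setting).

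**Results at 0.6 SD**

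| r | two-sample power | paired power | two-sample type I error | mean 95% CI half-width, two-sample | same, paired |
|---|---|---|---|---|---|
| 0 | 46% | 44% | 5.0% | 0.64 SD | 0.65 SD |
| 0.3 | 45% | 58% | 2.1% | 0.64 SD | 0.55 SD |
| 0.5 | 44% | 72% | 0.7% | 0.64 SD | 0.46 SD |
| 0.7 | 43% | 91% | 0.1% | 0.63 SD | 0.36 SD |

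The paired test keeps its type I error at 5% throughout.

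**Other shifts, r = 0.5**

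| shift | two-sample power | paired power |
|---|---|---|
| 0.4 SD | 16% | 40% |
| 0.6 SD | 44% | 72% |
| 0.8 SD | 76% | 92% |
| 1.0 SD | 94% | 99% |

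**Rank tests, one swab measure before and after at one site.** With the same assumptions (0.6 SD, r = 0.5), rank-sum has about 42% power and signed-rank about 70%. This takes 20 patients with swabs, which the documents do not establish. Protocol 5.1 speaks of all sites for the clinical tests but assigns swabs to one named site, while Protocol 4 describes a single clinical site. The number with swabs may be below 20.

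**Direction.** The overstatement factor exceeds 1 whenever r is above 0. With positive correlation an independent-sample test of a within-patient contrast therefore rejects less often than 5% when nothing has changed, as the type I error column shows.

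**The case against.** The strongest reply is that only an adjective is missing. The SAP describes one cohort measured twice, a paired t test is a Student's t test, and it is the natural choice for that design. Means with SDs at each time are ordinary descriptive summaries. The SAP also looks at change in individual patients' Oxford grade, so within-patient change was in view. The rank tests are introduced as examples for various groups, so paired ones are not excluded. Rank-sum would be valid for comparing protocol 1 with protocol 2, given one value per patient.

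All of that stands, and it limits the point to under-specification. For the t test alone, the point is close to a clarification. The size is also conditional: it needs the less natural reading, a material correlation and a moderate effect, and it shrinks to 5 points at 1.0 SD with correlation 0.5.

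What the reply does not remove is the microbiome half, where both named examples are independent-sample tests and neither PERMANOVA nor ZINB is tied to the patient.

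A reader might infer two stronger things. One is that the SAP has chosen the wrong test; the text does not say which form of t test is meant, so this is not shown. The other is that the wording would yield false claims of improvement; with positive within-patient correlation the error runs the other way.

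**Conclusion.** The point holds as a gap in specification that is worth closing. The data are repeated within patient, and neither document names an analysis that says so.

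If independent-sample tests were used for before/after, or for sites within a patient, the cost would be lost power and wider intervals. At 20 patients and a 0.6 SD shift the power lost is 28 points at correlation 0.5 (44% against 72%) and 13 points at 0.3 (45% against 58%). At correlation 0 nothing is lost. The shift, the correlation and normality are assumptions; only the 20 and the 0.05 come from the documents. These percentages show the cost of one reading and are not an estimate of the study's actual power. No size is claimed for the PERMANOVA or ZINB analyses, which were not simulated.

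**What to change.** **Clinical outcomes.** State that the test is a paired t test, or a Wilcoxon signed-rank test, on each patient's follow-up minus baseline change. Report the mean change, SD of change, 95% confidence interval and the number of patients without both values.

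**Microbiome**
- Alpha diversity, before against after at one site: signed-rank.
- Beta diversity: PERMANOVA with permutations restricted within patient. Bray-Curtis, Jaccard and Jensen-Shannon are distances between samples, not one value per patient per visit, so signed-rank cannot be applied to them directly.
- Taxa: ZINB with a patient random effect.
- Rank-sum and Kruskal-Wallis: keep for groups that are independent, such as protocol 1 against protocol 2.
- Environmental control: it is not a patient site, so give it its own stated comparison outside the patient blocking.

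**Cost.** SAP wording only, with no new data, visits or patients. If pairing was always intended, one sentence settles the t test. There are two downsides: about 2 points of power are lost if the before/after correlation is near zero, and only patients with both values contribute.

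### No test is named for Oxford staining grade and individual change is only described; name a paired ordinal test on the grades already being collected

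*SAP*

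**What the plan says.** The clinical part of the SAP treats two kinds of outcome differently.

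- For the SPEED and VAS scores, means before and after treatment are calculated and "a student's T test will be used to assess whether there is a significant difference", at the 0.05 level. The same is planned for tear osmolarity, basal tear production and tear break-up time. Whether the t test is paired is not stated.
- For staining: "The proportion of patients in each category of the oxford scale for fluorescein grading (I-V) will also be compared at baseline and post-treatment". No test and no significance level is attached to that sentence. It ends by saying that "the change in grade of individual patients will be assessed descriptively".

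The protocol fixes what data there will be. Section 5.1 lists "staining pattern on cornea (using oxford scale) with Fluorescein" among the baseline tests. Section 5.3 repeats, four weeks after the final treatment, "the same DED diagnostic measurements and tests that were done at baseline". On size, Section 3.1 says only that "a minimum of twenty subjects will be treated to detect improvement after BBL treatment for DED". No power, effect size, expected grade distribution or within-patient correlation is given.

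**The concern.** The Oxford grade is an ordered scale, measured twice in the same people. Most of the information on treatment effect lies in how far each patient moves. The plan compares the totals in each category and gives no inference to the movement.

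The sentence leaves two readings.

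- **A test is intended.** It is then unspecified and could be chosen after the data are seen. The obvious choice for proportions in five categories at two times is a chi-square or Fisher test on a 2x5 table. That takes the two time points as independent groups and the grades as unordered labels. With 20 patients it has on average 20/5 = 4 patients per cell.
- **No test is intended.** Staining then has no planned inference, while the two questionnaires and the three named tear measures each get one.

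The trial is open-label, so self-reported symptoms are open to expectation effects, and clinical signs help a reader to interpret them. A non-significant staining result that came from an insensitive test could be misread as no change in staining.

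**Working it through.** **Plan's own figure.** There is none to reproduce: the minimum of 20 has no stated power or effect size, and no power is given for staining.

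**Inputs.** From the documents: n = 20 (Protocol 3.1), five grades (SAP), the same subjects at both times (Protocol 5.1 and 5.3), and 0.05 as the level used for the other clinical outcomes. Assumed: two-sided testing, no dropout, one grade per patient, the baseline grade distribution, the within-patient correlation rho and the size of the shift.

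**Worked example, free of any effect-size or correlation model.** Suppose 8 of 20 patients improve by one grade, 12 are unchanged and none worsen. The counts in grades I to V go from 2/5/7/4/2 to 4/6/6/3/1.

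- *Unpaired chi-square.* The expected counts are half of each column total: 3, 5.5, 6.5, 3.5, 1.5. The statistic is 2 x (1/3 + 0.25/5.5 + 0.25/6.5 + 0.25/3.5 + 0.25/1.5) = 0.667 + 0.091 + 0.077 + 0.143 + 0.333 = 1.31 on 4 df, p = 0.86.
- *Exact paired test.* All 8 changes are equal in size and direction, so the sign and signed-rank tests agree: p = 2 x 0.5^8 = 0.0078.

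**Power by simulation.** Model: latent severity is bivariate normal with correlation rho, cut at its quintiles so that baseline grades are even. The post-treatment value is lowered by a shift of d SD. With cut points c, the mean change in grade is the sum of [Phi(c + d) - Phi(c)] over the four cuts. For d = 0.6 this is 0.204 + 0.236 + 0.203 + 0.125, or about 0.77 grade. For d = 1.0 it is about 1.2 grades.

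| Shift | rho | 2x5 chi-square | Signed-rank | Share of power lost |
|---|---|---|---|---|
| none | 0.5 | 2.4% | 4.6% | - |
| none | 0.7 | 1.7% | 4.9% | - |
| 0.6 SD (about 0.75 grade) | 0.5 | 17% | 60% | (60 - 17)/60 = 72% |
| 0.6 SD | 0.7 | 13% | 79% | (79 - 13)/79 = 84% |
| 1.0 SD (about 1.2 grades) | 0.5 | 59% | 94% | (94 - 59)/94 = 37% |
| 1.0 SD | 0.7 | 57% | 99% | (99 - 57)/99 = 42% |

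Repeat runs at 0.6 SD put the chi-square at up to 19% (rho 0.5) and 15% (rho 0.7), hence the range 13-19%. The 1.0 SD rows use the exact signed-rank test. That version is slightly conservative on tied grades (null rejection 3.6-3.9%), so at 0.6 SD expect it to fall a few points below 60-79%.

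**Which feature matters.** At rho 0.7 and a 0.5 SD shift, power is 8% for the chi-square (neither feature), 20% for Stuart-Maxwell (pairing only), 21% for rank-sum (order only) and 59% for exact signed-rank (both).

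**Sensitivity to the baseline grades.** With grades spread 10/25/30/25/10 or 30/35/20/10/5 per cent, at 0.5 and 0.75 SD shifts, the chi-square loses 61-88% of the signed-rank power.

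**Floor of the paired test.** If all changes go one way, six changed patients give p = 2 x 0.5^6 = 0.031 and five give 0.0625. So at least six must change for significance.

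**The case against.** The strongest reply is that the SAP does not contain the test being criticised. A reader might infer that the plan prescribes an unpaired, unordered analysis. It does not: it names no test and states no independence assumption. Category proportions in the same patients can be compared with a paired, ordered marginal homogeneity test. Under the same model that test has 61% and 79% power at 0.6 SD (rho 0.5 and 0.7), matching signed-rank. This stands. The chi-square figures are conditional on the natural reading, and the firm finding is that the test is unspecified.

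Second, the sentence may be meant as description only, in which case power and type I error have no object. That is possible, but staining is then left without inference and the remedy is the same.

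Third, a reader might infer that a real improvement would go unseen. The documents do not support that. Individual change will be described, and a clear majority of improvers would show. What is missing is a pre-specified inference on it.

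Fourth, the size depends on assumptions. A general claim that most of the power is lost is not supported: at a 1 SD shift the loss is about 26-42% over rho 0 to 0.7. At rho 0 pairing adds nothing, and the gain comes from grade order alone. The low null rejection is also conservative, so it brings no excess of false positives, and it is 4.6% at rho 0.

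Fifth, staining might be taken for a main outcome. Neither document ranks the outcomes; it is one of several diagnostic tests.

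**Conclusion.** The point holds in a conditional form. What is certain from the documents is that the only planned comparison for staining is of category proportions, that no test is named for it, and that within-patient change is descriptive although paired ordered grades will be collected.

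If the comparison is run as an ordinary chi-square, the loss is large for modest effects: about 13-19% power against 60-79% at a shift of about 0.75 grade. It is smaller, about 40% of the signed-rank power, at about 1.2 grades. Under no change the chi-square rejects only about 2% of the time. These figures rest on n = 20, even baseline grades and rho 0.5-0.7, and only the 20 comes from the documents.

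The change is worth making under either reading, because a better method is available from data already planned. It improves the before-after comparison only. With no untreated control, a significant change in grade would still not separate treatment effect from regression to the mean or other change over time.

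**What to change.** Replace the staining sentence in the SAP with text to this effect:

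- The test for staining is an exact two-sided Wilcoxon signed-rank test, at the 0.05 level, on each patient's change in Oxford grade from baseline to the visit four weeks after the last treatment.
- Report the median change, the numbers improved, unchanged and worse, and the number of patients with both grades. Say how missing follow-up is handled.
- Keep the table of category proportions as description.

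Three definitions must accompany it:

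- How two eyes become one value per patient. The documents do not say which eye is used.
- Which pre-treatment exam is baseline. Protocol 5.1 describes run-in as the collection of baseline values, but Section 4 also has a full exam at the treatment visits.
- Whether the Benjamini-Hochberg adjustment, stated at the end of the microbiome text but worded for all comparisons, covers this test.

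The same edit could state whether the t test for the other outcomes is paired. The cost is a few SAP sentences, best settled before any follow-up grades are analysed. No new data, visits or patients are needed.
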